10.3. Data collection

10.3.1. 4DCT data and radiation dose distribution data

10.3.2. Respiratory surrogate data. Collected from standard treatment techniques, used to assess tumor motion through time and space.

10.3.3. Daily images acquired for patient alignment and motion management. Collected from standard treatment techniques.

10.3.4. RTOG toxicity data and constitutional symptoms

10.3.5. Pulmonary function tests, including FEV, FEV1 and DLCO.

10.3.6. Patient self-assessment

10.3.7. RTOG acute radiation morbidity scoring scheme. Utilized for RTOG 9311, these criteria will be reviewed at radiation therapy *fini* and at the 3-month post-radiation follow-up appointment.

10.3.8. RTOG late radiation morbidity scoring scheme. Utilized for RTOG 0117, these side effects will be collected at follow-up visits after 90 days post-radiation.

11. STATISTICAL CONSIDERATIONS

11.1. Study Design/Endpoints

The primary endpoint of this study will be the ratio of the tissue elasticity map following RT to the elasticity map before RT (i.e., the Jacobian ratio of (post RT /pre RT)) calculated from 4DCT at 3 months post-RT. Based on the randomness of our measurement technique, diminished expansion is defined as a Jacobian ratio <0.94 (i.e., less than 94% of the pre-RT value). Data for the analysis will consist of the voxel-specific ratios of tissue elasticity measures from scans being compared. The primary and secondary endpoints at 3, 6, and 12 months post-RT include: (i) the volume of lung where diminished expansion occurs (Jacobian ratio (post RT /pre RT) <0.94), (ii) the volume of lung where expansion is improved (Jacobian ratio (post RT /pre RT) >1.06), (iii) the volume of lung where “meaningful” expansion occurs (Jacobian post-RT > 1.1), and (iv) clinically observed pulmonary toxicity determined by PFT endpoints, and (v) changes in inflammation as determined from blood serum.

Some subjects may have multiple sites of disease treated within the thorax. Since these subjects will be treated at all sites with either the control (Arm 1) or experimental (Arm 2) treatment plan, and since the primary endpoint of the study is the assessment of normal lung tissue response to delivered radiation, these subjects represent a single sample within our analysis.

Power analysis shows the planned enrollment of 60 subjects per cohort will ensure 90% power to detect mean difference of 4% in the lung tissue elasticity (percentage of the lung with a Jacobian ratio post-RT/pre RT < 0.94), based on 6.3% deviation in this measure from 13 subjects in our preliminary data. If the normality assumptions of ANOVA are not satisfied, nonparametric rank-based tests will be used instead. All statistical tests will be two-sided and assessed for significance at the 5% level, and will be performed by the UW-Madison Department of Biostatistics and Medical Informatics.

Update as of 2/3/2021: The statistics are based on 30 subjects reaching the 3 month followup time point. To date 106 have been enrolled but 14 did not complete the 3 month imaging time point. Therefore we are adding numbers to replace those subjects and to allow an additional 5 subjects to ensure we complete the protocol and meet the study objectives.

REFERENCES

1. American Cancer Society. *Cancer Facts & Figures 2015*. Atlanta: American Cancer Society; 2015.

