5.2. Baseline Research Assessments

- 5.2.1. **4DCT.** This is ordered in addition to the standard 4DCT performed for RT-simulation
- 5.2.2. **Patient self-assessment.** Assessment is based on a modified Borg scale, which has a history of use in pulmonary labs, with a scale of 1 (resting comfortably in a chair with no effort) to 10 (the most exertion and difficult breathing ever experienced)
- 5.2.3. **RTOG defined acute toxicity evaluation.** Evaluate both lung and esophageal toxicity (Appendix B)
- 5.2.4. **RTOG late toxicity evaluation.** Evaluate lung, esophageal, skin, subcutaneous tissue, spinal cord, heart, and bone (Appendix C)
- 5.2.5. **Constitutional assessment:** quantify nausea, vomiting, diarrhea and other symptoms prior to initiating chemoradiation and any medications used for these symptoms

5.3. 4-Dimensional Computed Tomography (4DCT) Imaging

4DCT imaging is performed at simulation (treatment planning) in all patients. This first 4DCT is clinically indicated for radiation simulation as a standard procedure. This clinical imaging data will also be used for research in this protocol to evaluate the biomechanical tissue elasticity of the lungs. Lung tissue elasticity is being used as a surrogate for ventilation, which in turn is a component of pulmonary function. Because the goal of the research arm is to reduce pulmonary function damage, changes in lung tissue elasticity will be quantified using 4DCT and it's essential the changes observed be distinguished from random changes in our measurement. Consequently, each subject will receive two 4DCT scans at each time point in order to quantify the repeatability of the measure of tissue elasticity and to demonstrate the changes following RT are greater than the expected variation from the procedure itself. The results from both 4DCT scans will

be used by taking the geometric mean of the tissue elasticity measures of scan 1 and scan 2 at each time point.

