10.2.3. Repeatability of 4DCT based measures of lung tissue elasticity

10.2.3.1. Variation of the tissue elasticity calculated between scan 1 and scan 2 at each time point will be quantified and compared to longitudinal changes in tissue elasticity.

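### The noise floor measurable from each subject's two pre-RT scans is not a covariate in the primary comparison; adjusting for it could recover some power at almost no cost.

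*Combined protocol and SAP*

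**What the plan says.** Sections 1.1, 10.1 and 11.1 base the primary endpoint on the post-RT/pre-RT Jacobian ratio at 3 months, and the power statement in 11.1 works with the percentage of lung below 0.94. The cut comes from measurement error and is the same for everyone: "Based on the randomness of our measurement technique, diminished expansion is defined as a Jacobian ratio <0.94". The plan does not say how many error SDs the 6% represents.

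Section 5.3 explains the repeat scans: "each subject will receive two 4DCT scans at each time point in order to quantify the repeatability of the measure of tissue elasticity". It then says that the geometric mean of the two scans' elasticity measures is taken at each time point. Section 11.1 does not repeat that step.

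The difference between the two scans appears as an outcome only in Section 10.2.3, a secondary endpoint: "Variation of the tissue elasticity calculated between scan 1 and scan 2 at each time point will be quantified".

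The primary test in Section 11.1 is an ANOVA with a fallback: "If the normality assumptions of ANOVA are not satisfied, nonparametric rank-based tests will be used instead". No covariate is named. The sizing reads "Power analysis shows the planned enrollment of 60 subjects per cohort will ensure 90% power to detect mean difference of 4" percentage points, "based on 6.3% deviation in this measure from 13 subjects in our preliminary data", and "All statistical tests will be two-sided and assessed for significance at the 5% level".

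**The concern.** A fixed cut turns measurement error into counted lung. With no true change at all, some voxels still fall below 0.94, and their number rises steeply with the subject's own scan error, for instance from irregular breathing or poor registration. If that error differs between subjects and partly persists from baseline to month 3, part of the spread in the primary percentage is noise that a pre-treatment measurement could predict.

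That measurement can be derived from data the trial collects anyway. Both pre-RT scans are acquired at simulation (Section 5.7.1), registration follows simulation (Section 4), and treatment cannot affect them. Leaving the covariate out of the primary model gives up whatever precision it would bring. This matters more in a cohort of 60 split 30:30, where the amendment text in Section 4.1 reports accrual of one subject every 4 to 8 weeks.

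**Working it through.** **Inputs.** Difference 4 points, SD 6.3 (reading the stated deviation as an SD), two-sided 5%: Section 11.1. Split 30:30 within a cohort of 60: Section 4.1, hypofractionation cohort. The within-arm correlation ρ between the pre-RT noise floor and the 3-month percentage is not in the documents; values of 0 to 0.6 are shown.

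**Step 1: the plan's own figure.** SE = 6.3 × √(2/n).
- n = 30 per arm: SE = 1.627, 4/1.627 = 2.459, power by noncentral t (58 df) 67.7%; the normal approximation gives 69.1%.
- n = 60 per arm: SE = 1.150, 4/1.150 = 3.478, power 93.2%.

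Neither is the stated 90%, which needs 54 per arm by the t calculation. That mismatch is a separate matter; here these two values are only the starting points.

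**Step 2: how much lung falls below 0.94 by noise.** Assume independent log-normal voxel error with single-scan SD s. The geometric mean of two scans has log-SD s/√2, so the post/pre ratio of two such means has log-SD s. With no true change, the share below the cut is Φ(ln 0.94 / s), with ln 0.94 = −0.0619. For s = 2%, 3%, 4%, 5% and 6% this is 0.1%, 2.0%, 6.1%, 10.8% and 15.1%.

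The same sum can start from where the cut was placed. If 6% was 1.96 SD of a single-scan ratio, 2.5% of voxels fall below it, and 0.3% after averaging. At 1.645 SD the figures are 5.0% and 1.0%; at 1 SD, 15.9% and 7.9%.

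**Step 3: power after adjustment.** Residual SD = 6.3 × √(1 − ρ²), with one degree of freedom fewer.

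| ρ | Residual SD | Power, 30 vs 30 | Power, 60 vs 60 |
|---|---|---|---|
| 0 | 6.30 | 67.6% | 93.2% |
| 0.2 | 6.17 | 69% | 94% |
| 0.4 | 5.77 | 75% | 96% |
| 0.5 | 5.46 | 80% | 98% |
| 0.6 | 5.04 | 86% | 99% |

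At ρ = 0 and 30 per arm, the lost degree of freedom costs less than 0.1 point of power.

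**Step 4: what ρ might be.** Hold the total SD at 6.3 and let each subject's noise persist fully to month 3. If 0.94 was a 1.96-SD single-scan limit (s = 0.0619/(1.96 × √2) = 2.2%), a between-subject log-SD of s of 0.20, 0.30 or 0.35 gives R² of 2%, 7% or 12%, and power at 30 versus 30 of 68%, 71% or 73%. At a 1.645-SD limit, power is 70% to 80%. With a median s of 3.5%, where the cut is only 0.0619/(0.035 × √2) = 1.25 SD, power runs from 73% to over 90%, depending on the spread and persistence assumed. The documents do not say which case applies.

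**Step 5: adjust, do not subtract.** Subtracting a floor with between-subject SD f gives variance 6.3² + f² − 2ρ × 6.3 × f. With f = 3 and ρ = 0 the SD is √(39.69 + 9) = 6.98, and power at 30 versus 30 falls from 69.1% to 60.3% (normal approximation). Subtraction helps only if ρ exceeds f/(2 × 6.3), here 0.24. It would also tend to remove too much, because the baseline pair compares single scans (log-SD s√2) while the endpoint compares averaged ones (log-SD s).

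**The case against.** An unadjusted ANOVA in a randomised trial is valid, so a missing covariate is not an error. Noise is expected to be similar in the two arms, and chance imbalance is already in the standard error. All of this stands.

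Three stronger readings are tempting, and the documents do not support them.
- A reader might infer that the repeat scans play no part in the primary analysis. Section 5.3 puts both into the elasticity measure through their geometric mean, which cuts voxel error by up to √2.
- A reader might infer that noise voxels push the trial below its computed power, or bias the arm difference. Section 11.1 defines both the 4 points and the 6.3 on the observed percentage, which already includes noise.
- A reader might infer a large gain, for instance because subjects with s of 2% and 6% would differ by 15 points with no radiation effect. Neither value is documented, nor is the spread of noise between subjects. If the cut is close to a 1.96-SD limit, the gain at 30 versus 30 is only about 0 to 5 points.

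It is also fair to say that two scans in one session may understate noise across 3 months, which lowers ρ. A covariate need not measure that noise without error, but a weak correlation means a small gain.

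**Conclusion.** The point holds as an efficiency point. The plan collects a per-subject, pre-treatment measure from which the noise floor can be derived, and does not use it in the primary comparison. At 30 versus 30 the gain is about 2 points of power at ρ = 0.2, 7 at 0.4, 12 at 0.5 and 18 at 0.6. At 60 versus 60 it is at most about 6 points. These figures take 6.3 as the SD of the endpoint as it will be computed; Section 11.1 does not say whether the 13 preliminary subjects had single or averaged scans. The size cannot be settled from the documents, because ρ is not reported.

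The no-bias statement relies on randomisation. Section 4.1 assigns the next 8 conventional-fractionation subjects to the optimised plan without it. Baseline adjustment may help a little there but does not replace randomisation.

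**What to change.** In Section 11.1, make the primary analysis an ANCOVA of the 3-month percentage of lung with Jacobian ratio below 0.94 on arm and the subject's pre-RT noise-floor percentage. Define that percentage as the share of lung with scan 2/scan 1 below 0.94, averaged with the share for scan 1/scan 2. Run the model within each fractionation cohort, since power is stated per cohort, or with a fractionation term if the cohorts are pooled. Enter the floor as a covariate; do not subtract it.

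Fix the covariate's definition before the arms are compared, and state what is done if one pre-RT scan is unusable. Keep the unadjusted ANOVA or rank test as a sensitivity analysis. Repeat in Section 11.1 that the maps are geometric means of both scans, with a reference to Section 5.3.

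The cost is one paragraph and one extra ratio map per subject from scans already planned. No additional patients or procedures are needed, and the target remains the arm difference in the mean percentage.

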1. OBJECTIVES

1.1. Primary Objective

This clinical trial sets out to determine if subjects who have been treated with radiation therapy plans designed to spare high ventilation regions have superior preservation of pulmonary function compared to those treated with standard radiation dose distributions. Four dimensional computed tomographic imaging (4DCT) will be used to determine lung tissue elasticity, as required for ventilation. Lung tissue elasticity maps at 3 months after RT will be compared to those prior to RT, and used to quantify the change in the lung elasticity maps. Reduced lung tissue elasticity is defined in this study as a >6% reduction in expansion when compared to the baseline; the amount of lung tissue showing a >6% reduction is the metric for our primary endpoint, and will be tested for a significant difference between the two arms.

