Esophagus: The mean dose to the esophagus is optimally kept below 34 Gy.[47] This is not an absolute requirement, but is strongly recommended unless other, more critical constraints force the situation. The V60 (% volume of esophagus exceeding 60 Gy) should be calculated for each patient for standard fractionation. Doses for hypofractionation will follow recommendations in RTOG 0618, 0813, or 0915 based on fraction size.

Heart: The following limits are recommended: 60 Gy to $<1/3$, 45 Gy to $<2/3$, and 40 Gy to $<100\%$ of the heart for standard fractionation. Doses for hypofractionation will follow recommendations in RTOG 0618, 0813, or 0915 based on fraction size.

5.5.4. Research Arm (Arm 2) Only - Planning strategy to reduce pulmonary function damage.

Subjects in the second arm will also receive treatment plans that meet all the criteria of the first arm, but their treatment plans will include strategies to reduce pulmonary function damage following radiation therapy. The strategy to reduce pulmonary function damage, described below, will be implemented during treatment planning. In brief, radiation dose distributions will be designed to “redistribute” the radiation dose away from lung regions with high tissue elasticity. Lung tissue elasticity is calculated from measures of tissue expansion that occurs during respiration. Specifically, the Jacobian determinant of the transformation matrix between the CT scan acquired when the subject has reached the end of exhale and the scan acquired when the subject has reached the end of inhale. These images, which are extracted from the 4DCT data, allow the creation of lung tissue elasticity maps like the ones shown in Figure 3 below.

[figure not shown]

Figure 3. Map of lung tissue elasticity, where a Jacobian value of 1.0 (green) indicates no tissue expansion. The higher the Jacobian value (red end of scale) the greater tissue expansion.

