Subjects randomized to this arm of the trial will have the same prescribed radiation dose to the tumor volume and held to the same radiation dose criteria as the subjects in the standard of care arm. The fundamental difference will be radiation doses for these subjects will be redistributed away from regions predicted to cause the greatest reduction in pulmonary function if damaged. For example, to treat the tumor in the images above (slightly medial to the dashed blue lines), circumferential radiation beams restricted to the lower lobes of the lung (green regions) would be chosen over beams that enter or exit the higher tissue expansion regions of the right middle lobe or right upper lobe (blue & purple regions).

Pre-radiation therapy 4DCT images (Section 5.3.1) will be used to identify regions-of-interest (ROI) uniquely utilized in this planning strategy. These ROIs including anatomical regions (airway tree, pulmonary vasculature, heart, and lobar regions of the lung) and functional regions (regions of the lung discretized by the amount of tissue expansion that occurs during ventilation). Although tissue expansion is determined at a 1mm^3 resolution, the ROIs will be grouped in 0.05 bins of expansion (typically from 1.05 up to 1.5). Airway tree branches and pulmonary vasculature supporting lung regions of high tissue expansion will be preferentially avoided as well. Radiation therapy treatment planning will be calculated using an inverse optimization technique, relying on dose objectives specified for each ROI. The penalty or “cost function” for failing to meet the specified dose objective will increase linearly with radiation dose, while the weight for each cost function will be determined from the slope of the dose response curve for each ROI. The inverse optimization algorithm will minimize the sum of the cost functions for all dose objectives created in the treatment plan. These dose objectives will be added to the dose objectives utilized in the conventional arm of this study (Sections 5.5.1 – 5.5.3).

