10.1. Primary endpoint

Lung tissue elasticity changes. The primary endpoint of this study will be the ratio of the tissue elasticity map following RT to the elasticity map before RT (i.e., the Jacobian ratio of (post RT /pre RT)) calculated from 4DCT at 3 months post-RT. Based on the randomness of our measurement technique, diminished expansion (i.e. substantial change) is defined as a Jacobian ratio <0.94 (i.e., less than 94% of the pre-RT value).

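### Is the primary variable left open because section 11.1 lists a volume of lung but powers a percentage, and because section 1.1 calls a 6% fall in the Jacobian a 6% loss of expansion?

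*Combined protocol and SAP*

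**What the plan says.** The primary variable is described in several ways.

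- Section 1.1: "the amount of lung tissue showing a >6% reduction is the metric for our primary endpoint". No unit is given.
- Section 10.1 and the opening of section 11.1: the endpoint is the post-RT to pre-RT Jacobian ratio map at 3 months, with a ratio below 0.94 counted as diminished expansion.
- Section 11.1, item (i) of a combined list of primary and secondary endpoints: "the volume of lung where diminished expansion occurs".
- Section 11.1, power statement: a mean difference of 4% in the "percentage of the lung with a Jacobian ratio post-RT/pre RT < 0.94". The same sentence gives the source of the assumed variability: "based on 6.3% deviation in this measure from 13 subjects in our preliminary data".

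On the cut-off, section 1.1 says "Reduced lung tissue elasticity is defined in this study as a >6% reduction in expansion when compared to the baseline". Section 10.1 sets the limit at a Jacobian ratio of 0.94, "Based on the randomness of our measurement technique". Section 5.5.4 states that "a Jacobian value of 1.0 (green) indicates no tissue expansion", but it also says that "the ROIs will be grouped in 0.05 bins of expansion (typically from 1.05 up to 1.5", which applies the word expansion to the Jacobian value itself.

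**The concern.** A map, a volume and a percentage are different objects. A volume in mL depends on lung size and a percentage does not, so the two can rank subjects differently. The 4% difference and the 6.3% deviation apply only to the percentage.

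The percentage also needs a denominator. Section 5.5.3 contours the right and left lungs separately. It defines total lung as lung less the CTV only within the standard-fractionation dose limit, and it refers the hypofractionation limits to other protocols. If the unit or the mask were chosen after the data were seen, the primary test would carry an analyst's choice.

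The wording in section 1.1 raises a second worry. If no expansion is J = 1.0, then expansion is J − 1, and a 6% fall in J is a much larger relative fall in J − 1. A reader could take the result to mean that the affected lung lost just over 6% of its expansion.

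**Working it through.** **1. The plan's power figure.** Inputs from section 11.1: difference δ = 4, SD σ = 6.3, two-sided 5%, 60 per cohort, stated power 90%. With n per arm, power = Φ(δ / (σ√(2/n)) − 1.96).

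- n = 60: 4 / (6.3 × 0.1826) = 3.478; 3.478 − 1.960 = 1.518; power 93.5% (noncentral t: 93.2%).
- n = 30: 4 / (6.3 × 0.2582) = 2.459; 2.459 − 1.960 = 0.499; power 69.1% (noncentral t: 67.7%).

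Neither equals 90%. Section 4.1 shows a cohort of 60 split 30 and 30, so the gap between 69.1% and 90% is a real question. It is separate from this one, because naming the unit moves neither figure.

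**2. Percentage against volume.** The documents give no SD in mL and no lung volume, so power for a volume cannot be calculated from them. As an illustration, assume that lung volume has a CV of 20–30%, that the mean affected share m is 5–25%, that the two are independent, and that the difference is 4% of mean lung volume. The effective SD is √[(1 + CV²)(6.3² + m²) − m²].

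- m = 5, CV 20%: √(1.04 × 64.69 − 25) = 6.5; power 92% (60 per arm) or 66% (30 per arm).
- m = 25, CV 30%: √(1.09 × 664.69 − 625) = 10.0; power 59% or 34%.

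This loss arises only if an absolute volume is tested, and section 11.1 does not power that variable.

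**3. Which variable the plan tests.** Section 11.1 says the analysis data are voxel-specific ratios. The share of voxels below 0.94 is a direct per-subject summary of the map, so the map and the percentage are input and output. The power sentence is the only one with a difference and an SD, and it describes the SD as belonging to the same measure. Elsewhere the protocol also expresses a volume as a share: V20 in section 5.5.3 is a volume stated in percent, and section 10.2.1.2 uses fraction in its title and volume in its text.

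**4. Which lung.** Sections 5 and 11.1 both describe the primary endpoint as the response of normal lung, which argues for leaving the tumour out. Section 2.2 sets out to quantify change in treated and untreated lung and shows loss crossing into the right lung from a left-sided tumour, which argues for both lungs. Section 11.1 treats a subject with several thoracic sites as one sample, which fits a whole-lung measure. Section 5.5.3 contours each lung separately but then applies its limit to the two together.

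**5. The 6% wording.** At a ratio of 0.94, the share of J − 1 lost is 0.06J / (J − 1).

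- J = 1.50: 0.090 / 0.50 = 18%.
- J = 1.25: 0.075 / 0.25 = 30%.
- J = 1.10: 0.066 / 0.10 = 66%.

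Conversely, a literal 6% loss of J − 1 at J = 1.25 gives a ratio of (1 + 0.94 × 0.25) / 1.25 = 0.988. That lies well inside the 0.94 to 1.06 band outside which the plan counts change, so the literal reading cannot be the intended rule. If expansion means J, as in the bins of section 5.5.4, section 1.1 and the 0.94 rule agree.

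**The case for a change.** The best argument for a change is that a probable intention is not a specification. No sentence states the mask, and the hypofractionation cohort, 60 of the 120 planned subjects, has no local lung-volume definition to borrow. The figures in section 2.2 show a tumour present before RT and absent after, so the treatment of target voxels is a real choice. Section 4.1 assigns the next 8 conventional-fractionation subjects to the optimized arm without randomization, so lung size could differ between arms. Settling the wording would cost little.

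Part of this stands: the mask is not written down, and nothing in the documents confirms which mask gave the 6.3%. The rest is weaker. An imbalance in lung size bears mainly on a volume, and the powered variable is a percentage. A one-lung denominator would miss the cross-lung effect that motivated the study. The preliminary measure also gives analysts a precedent to carry forward.

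On the wording, it can be said that at a baseline J of 1.05 complete loss of expansion gives 1.00 / 1.05 = 0.952 and goes uncounted. But section 2.2 reports 0.96 in affected lung after RT. Read as a Jacobian, that gives 0.96 / 1.05 = 0.914, which is counted. In any case this would be a criticism of the noise-based threshold, which is not in dispute.

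**Conclusion.** No change follows. The natural reading is the per-subject percentage of normal lung, both lungs together, with a 3-month Jacobian ratio below 0.94. The missing mask is a detail that analysts would settle from the protocol's own statements and the preliminary measure. The phrase in section 1.1 is a clerical looseness: the rule that is computed is the same in sections 10.1 and 11.1.

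The effect on the stated design is nil if the percentage is kept on the scale of the preliminary 6.3%: power stays at 93.5% with 60 per arm and 69.1% with 30 per arm. The fall to between 92% and 59% (60 per arm) needs both an absolute-volume test and assumed lung-size variation. The 18% to 66% losses of J − 1 describe how the threshold reads in words and alter no result. The conclusion assumes that the 13 preliminary subjects were measured on the mask to be used in the trial; the documents call it the same measure but do not describe the mask.

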4. RANDOMIZATION PROCEDURES

Patients may not undergo protocol procedures prior to signing consent. All patients must meet eligibility criteria listed in Section 3 and provide written informed consent. The study coordinator will verify eligibility, assign a case number, and register the patient in the UWCCC ONCORE database after simulation and after all eligibility criteria have been met. Information to be recorded

The following information will be recorded for each subject enrolled:

- Protocol number
- Patient's name and initials
- Patient's medical record number
- Patient demographic data including gender, birth date and race.
- Signed patient consent forms
- HIPAA authorization form

4.1. Randomization between Therapy Arms 1 & 2

Patients will be randomized between two arms. Subjects in the first arm will receive conventional treatment planning as described in sections 5.5.1 through 5.5.3. Subjects in the second arm will also receive treatment plans that meet all the criteria of the first arm, but their treatment plans will include strategies to reduce pulmonary function damage following radiation therapy as described in section 5.5.4. Randomization will be performed by the data management team using a random number generator application (developed by Randomness and Integrity Services Ltd., Dublin, Ireland) that is a web based application that can also run on an Apple iPhone, iPad, or iPod touch running iOS 5.1.1 or later.

Amend 3/15/22

The Hypo-fractionation patient cohort has reached accrual of 60 subjects (30 conventional treatment planning, and 30 optimized planning).

The Conventional Fractionation cohort has accrued 46/60, however the treatment assignment of conventional treatment planning versus optimized planning is unbalanced, with 27 assigned to the standard dose specification planning and 19 assigned to the optimized treatment planning.

Accrual has significantly slowed and we are accruing 1 subject every 4-8 weeks. In light of the extremely low accrual we will assign the next 8 subjects to the optimized treatment plan to balance the study arms to ensure each arm has adequate enrollment for proper statistical analysis. When the arms are balanced, we will proceed with randomization via random.org until one arm reaches 30, then the remaining subjects will be placed in the remaining open arm.

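### The 90% power in section 11.1 holds for arms pooled over both fractionation cohorts (93%) but not within one cohort (68%), and the plan fixes neither the stratum's place in the analysis nor a single primary test

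*Combined protocol and SAP*

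**What the plan says.** All of the analysis method is in section 11.1 of the combined protocol and SAP.

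- **Sizing.** "the planned enrollment of 60 subjects per cohort will ensure 90% power to detect mean difference of 4% in the lung tissue elasticity", where the measure is the percentage of lung with a Jacobian ratio below 0.94. The deviation is given as 6.3%, from 13 preliminary subjects.
- **Level.** "All statistical tests will be two-sided and assessed for significance at the 5% level".
- **Test.** "If the normality assumptions of ANOVA are not satisfied, nonparametric rank-based tests will be used instead". This is the only mention of ANOVA. No factors, normality criterion or named rank test are given.
- **2021 update.** "The statistics are based on 30 subjects reaching the 3 month followup time point". It does not say whether this is per arm, per cohort or per cell.

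Elsewhere, the schema stratifies by fractionation before randomization, and section 5.5.1 plans 60 subjects of each type. Section 4.1 uses the word cohort for a fractionation stratum ("The Conventional Fractionation cohort has accrued 46/60") and allocates within that stratum "until one arm reaches 30, then the remaining subjects will be placed in the remaining open arm". Section 1.1 says only that the primary metric "will be tested for a significant difference between the two arms".

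**The concern.** Two things are left open.

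The first is which comparison carries the stated power. Read with section 4.1, 60 per cohort means 30 per planning arm within one fractionation type, and the 2021 figure of 30 fits that reading. Read with section 1.1, the comparison is between arms over all 120 subjects, which is 60 per arm. These differ by a factor of two in sample size. Within the pooled reading, the plan also does not say whether the stratification factor is a model term.

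The second is which quantity is estimated. Power is stated for a mean difference. If a normality check fails, the primary test becomes a rank test, which does not estimate that difference, and no effect measure is given for that case.

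Two analysts following section 11.1 could therefore run a pooled, a stratum-adjusted or a by-cohort comparison, each as ANOVA or as a rank test, and could reach different primary conclusions from the same data.

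**Working it through.** **Inputs.** Difference 4 points, SD 6.3 (read as a between-subject SD), two-sided 5%: section 11.1. Subjects: 60 per fractionation type (schema, section 5.5.1), 30 per planning arm within a type (section 4.1), hence 30 + 30 = 60 per arm when pooled.

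**1. The plan's own figure.** For a two-sample t-test with n per arm, SE = 6.3 × √(2/n) and the noncentrality is 4/SE. Power comes from the noncentral t distribution.

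| Comparison | n per arm | SE | 4/SE | Critical t | Power | Difference detectable with 90% power |
|---|---|---|---|---|---|---|
| Both cohorts pooled | 60 | 1.150 | 3.478 | 1.980 | 93.2% | 3.76 |
| One cohort alone | 30 | 1.627 | 2.459 | 2.002 | 67.7% | 5.36 |

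Power of 90% is reached at 54 per arm. The pooled comparison thus meets the stated 90% as a minimum, and the within-cohort comparison falls about 22 points short. A one-sided test would not rescue the within-cohort reading (78.4%).

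**2. Adding the stratum.** A model with arm and cohort uses one more degree of freedom. At the same residual SD, power at 60 per arm is still 93.2%.

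**3. Omitting the stratum.** Suppose 6.3 is the SD within a cohort, the cohort means differ by D, and each of the four cells holds 30 subjects. The arms are balanced on cohort, so the true SE of the arm difference stays at 1.150. The gap inflates the residual variance that the test uses: the residual sum of squares divided by 6.3² is noncentral chi-square with 118 df and noncentrality 120 × (D/2)²/6.3². The documents give no value for D, so a range is assumed.

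| Assumed D | Noncentrality | Power | Actual type I error |
|---|---|---|---|
| 4 | 120 × 4/39.69 = 12.1 | 91.8% | 4.0% |
| 8 | 120 × 16/39.69 = 48.4 | 86.8% | 2.0% |
| 10 | 120 × 25/39.69 = 75.6 | 82.5% | 1.2% |

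The test becomes conservative. If 6.3 already includes the gap between cohorts, nothing is lost against plan.

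**4. The switch of test.** The plan names neither a check nor a rank test. The simulation (10,000 runs, 60 per arm) assumed Shapiro-Wilk on residuals at p < 0.05, then Mann-Whitney, otherwise ANOVA. The shapes are also assumed.

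| Situation | With switch | Always compare means |
|---|---|---|
| No effect, same gamma shape (1, 2, 4) in both arms | 5.1, 5.2, 4.5% reject | about 5% |
| Uniform 4-point shift, gamma shape 1, 2, 4 | 99.6, 98.0, 95.5% power | 92.4, 92.6, 92.9% |
| Equal means, gamma (1, 2, 4) against normal | 11.4, 7.8, 5.9% reject | 4.9, 5.3, 5.0% |
| Mean benefit of 4 confined to 25% of subjects | 71.5% power | 79.2% |
| Confined to 33% | 82.2% | 83.3% |
| Confined to 50% | 88.4% | 88.5% |

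The last three rows take 6.3 as the SD of the arm without the affected subgroup.

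**The case against.** The strongest reply is that the intended comparison is clear enough. Section 1.1 compares two arms, the 120 planned subjects give 60 per arm, and that yields 93%. On this reading the trial is adequately powered, and that much stands. But section 4.1's use of the word cohort and the 2021 statement about 30 subjects point the other way, so the text does not settle it.

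Four stronger inferences are tempting and not supported:

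- *The trial has only 68% power.* No passage commits the primary test to a single cohort.
- *Only an unadjusted pooled test reaches 90%.* The model with the stratum reaches 93.2%, and the unadjusted test is the one that may fall below 90%.
- *Separate cohort tests create a multiplicity problem.* The plan states no rule under which either cohort, or both, must succeed, so there is no such error rate to compute.
- *The fallback inflates type I error.* With the same shape in both arms it does not, and for a uniform shift of skewed data it gains power. The 6 to 11% rejection needs a skewed arm against an exactly normal one; with two differently skewed arms of equal mean it was about 6%. The documents do not say which shape applies.

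It is also fair that the gap between 93% and 68% comes from the word cohort and the missing factors, and not from the sentence on rank tests. The design target is plainly a mean difference. What is open is only what would be estimated if the switch fires.

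**Conclusion.** The concern holds in a limited form. The 90% claim is sound for arms pooled over both fractionation cohorts (93%, with or without a stratum term at the same residual SD). It is wrong for a test within one cohort (68%, with 5.4 points detectable at 90% power), and the wording allows both readings. Leaving the stratification factor out costs nothing against plan if 6.3 includes the cohort gap. If 6.3 is a within-cohort SD, the test is conservative, with power of about 92%, 87% or 83% for assumed gaps of 4, 8 or 10 points.

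The normality-triggered switch is a separate and smaller matter. It is a possible change in what is estimated, and it bites only if sparing changes the shape of the damage distribution, for example by preventing large losses in a minority. These results rest on 6.3 being a between-subject SD, on balanced cells, and on the assumed gaps, shapes and normality check. This should be corrected, but it does not undermine the design.

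**What to change.** Before any comparison by arm, amend section 11.1 in three ways.

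1. State that the 90% power applies to the comparison of arms pooled over both fractionation cohorts, and that a test within one cohort has about 68%. If the sponsor did intend a within-cohort primary test, the power statement itself has to be rewritten.
2. Make the primary analysis a linear model of the percentage of lung with Jacobian ratio below 0.94 at 3 months, on arm and fractionation cohort. Report the adjusted mean difference with a 95% confidence interval and robust standard errors, whatever the distribution.
3. Replace the normality-triggered switch with a cohort-stratified rank test (van Elteren, for example) as a sensitivity analysis.

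The cost is wording only, because the stratum is already recorded. The stratum term takes one degree of freedom and leaves power at 93.2%. In simulation with cells of 30, the arm and cohort model with HC3 standard errors kept 92.9 to 93.4%. The downside is about 3 to 7 points of power forgone if the data are skewed and the effect is a uniform shift (95.5 − 92.9 = 2.6 up to 99.6 − 92.4 = 7.2). No further covariate is needed.
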